1.46 PRIMARY OUTCOME ANALYSES

The primary outcome (all-cause mortality or cardiovascular hospitalization) will be calculated by measuring time from randomisation until first event or last known event-free observation during the follow-up period as defined in 1.17.1. The primary analysis of the primary outcome will compare the randomised groups using a log-rank test statistic. Survival estimates will be presented using methods by Kaplan and Meier and the adjusted hazard ratio and 95% confidence interval presented using a cox proportional hazards model (or appropriate alternative where assumptions are not met). Superiority of CABG over PCI will be declared with a two-sided p-value <0.05 on the log-rank test. A secondary analysis of the primary outcome will follow the same methodology on the per protocol (PP) population.

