1.16 SIZE OF SAMPLE

STICH3-BCIS4 is a superiority trial powered for the primary outcome of survival time from cardiovascular hospitalisation and all-cause mortality. Using a time-to-event analysis to detect a HR of 0.7 with a 1:1 allocation ratio, 90% power, and a 2-sided alpha value of 0.05, a total of 414 events are required. Participants will receive a minimum of 4 years follow-up and 630 participants (n=315 in each arm) will be randomised in the UK.

The sample size is based on the following assumptions. **1.** A minimum clinically important treatment effect HR for CABG vs. PCI of 0.7 that is written within the range of treatment effects (0.63 to 0.74) observed in previous pragmatic RCTs of CABG versus PCI that have changed clinical practice (20-22). The proposed effect size was chosen as stakeholders felt that a large benefit would be required to convince clinicians of the benefits of more invasive treatment (CABG) in this high-risk population. **2.** Frequency of death or cardiovascular hospitalisation of 70% at 5 years in the PCI arm, from HES. To

calibrate this outcome, we compared the frequency of death or *heart failure* hospitalisation at 5 years in the STICH-1 matched HES cohort (42%) to event rates in both REVIVED and STICH trials (see Figure 1, from reference (8)). As heart failure hospitalisation is underestimated in HES data, the expected outcome frequencies are consistent. Coding for CV hospitalisation is more accurate and is included in the primary outcome for STICH3-BCIS4. **3.** A total study period of 89 months. **4.** An expected crossover rate of 8% typical for CABG vs. PCI trials; range 7-9%. (6, 7). **5.** Zero attrition due to the use of HES / Office for National Statistics (ONS) data for the primary outcome.

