1.26 METHOD OF IMPLEMENTING THE RANDOMISATION/ALLOCATION SEQUENCE

1.26.1 Randomisation

Randomisation with allocation concealment will utilise a centralised, web-based system (Sealed Envelope Ltd, London, UK). Participants will be randomised on the day of consent in a 1:1 ratio to either CABG or PCI stratified by centre and clinical presentation; acute versus chronic coronary syndrome.

The participant's initials, date of birth, and sex will be entered into the randomisation system which will generate the participant's randomised allocation (PCI or CABG) and unique participant identifier (Trial ID).

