1.33 EXPECTED SERIOUS ADVERSE EVENTS

The risk of intervention is not negligible. In the STICH trial, participants with ischaemic left ventricular dysfunction undergoing CABG had 5% mortality at 30 days post-surgery. In contrast, the peri-procedural risk of death following PCI should be less, although the overall burden of SAEs may be similar. In the SYNTAX trial (22) for example, the rate of Major Adverse Events at 30 days was the same in both CABG and PCI groups (only 7% of participant in this trial had iLVSD). However, with time, recurrent symptoms and repeat revascularisation are typically higher in the PCI treated patients, meaning that freedom from death or revascularisation is lower. This is evident in the Kaplan Meier curves in Figure 3, where the CABG curve (blue) is initially lower, but then crosses the PCI curve (red) after 3-6 months.

[figure not shown]

Figure 3 Freedom from death or cardiovascular hospitalisation in people with heart failure undergoing CABG or complex PCI in England 2013-2018, or matched to the STICH cohort (8)

However, other trials have identified important differences in early expected adverse events following both PCI or CABG (32). These include the risk of stroke, severe acute kidney injury (AKI), unplanned mechanical circulatory support for low cardiac output, major bleeding requiring intervention, or vascular complications requiring intervention. Along with early deaths, this information may be important for future patients with iLVSD who are deciding whether to undergo PCI or CABG. These early events may also be used by governance committees to establish whether there are any clinical differences in the number of these events versus expected event rates in normal practice. For this reason, we propose to collect the following SAEs occurring within 30 days of the date of surgery or the date of the first index PCI procedure, for review by governance committees.

1. Stroke
2. New onset end-stage renal failure defined as requiring dialysis
3. Unplanned mechanical circulatory support (IABP, Impella, VA ECMO)
4. Major bleeding requiring reoperation or re-hospitalisation
5. Major vascular complication requiring interventional radiology or surgical intervention
6. All-cause mortality

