1.50 MISSING VALUES

The primary outcome measures time until first event or censors at last follow-up therefore by definition there will not be any missing data. Other data adjusted for in the primary outcome analysis is a requirement of randomisation and therefore will not be missing. The use of routine and ONS data ensures we will have good long-term follow-up rates and early censoring due to loss to follow-up should be minimal at most and not expected at all. Analysis of non-time-to-event secondary outcomes like PROMs will be by complete case, the extent of missing data will be described.

HEALTH ECONOMIC EVALUATION

Evidence has shown that coronary heart disease cost £1.7 billion to the UK healthcare service, £2.4 billion in informal care, and £2.9 billion in productivity loss (34). The health economic evaluation will determine cost-effectiveness of CABG, compared with PCI, from the perspective of the UK NHS and personal social services, and the patient in line with the National Institute for Health and Care Excellence (NICE) guidance for health technology evaluation (35).

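### The stated 90% power assumes a constant HR of 0.7, but the protocol itself expects the curves to cross at 3-6 months, and the non-proportionality fallback does not reach the deciding log-rank test

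*Protocol*

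**What the plan says.** **Design.** Section 1.16: "Using a time-to-event analysis to detect a HR of 0.7 with a 1:1 allocation ratio", with "90% power, and a 2-sided alpha value of 0.05", "a total of 414 events are required", and "630 participants (n=315 in each arm) will be randomised in the UK". The listed assumptions are 70% PCI events at 5 years, 8% crossover, zero attrition and 89 months in total. No other effect pattern is considered.

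**Expected shape.** Section 1.33 describes Kaplan-Meier curves for freedom from death or cardiovascular hospitalisation, "where the CABG curve (blue) is initially lower, but then crosses the PCI curve (red) after 3-6 months". The Rationale says the same in general terms: early outcomes typically favour PCI and long-term outcomes favour CABG.

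**Analysis.** Section 1.46: "The primary analysis of the primary outcome will compare the randomised groups using a log-rank test statistic". Superiority is declared on the two-sided log-rank p-value. An adjusted Cox hazard ratio accompanies it, with an unnamed alternative if the model's assumptions fail. Section 1.10 also refers to a single HR, of 0.7 or less, in defining a positive trial.

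**Strata.** Section 1.26.1 has randomisation "stratified by centre and clinical presentation; acute versus chronic coronary syndrome". Section 1.50 adds: "Other data adjusted for in the primary outcome analysis is a requirement of randomisation". Section 1.46 names no strata for the log-rank test.

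**The concern.** Survival curves that cross cannot have a constant hazard ratio. The protocol therefore predicts that the assumption behind its event count will fail, for its own primary outcome, and treats that failure only as a contingency for the estimate. The log-rank test weights events equally over time, so early events against CABG offset later events in its favour. That lowers the chance of showing a real long-term benefit.

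Two things are at stake. The 90% power may not be delivered under the pattern the investigators expect. And a single HR would average early harm with later benefit, which is the trade-off that the Rationale says patients and clinicians must weigh.

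A smaller matter is that the HR is to be adjusted, apparently for randomisation factors, while the deciding test names none. The p-value and the confidence interval could then fall on opposite sides of significance.

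**Working it through.** **1. The protocol's own figure.** Schoenfeld: events = 4(z₀.₉₇₅ + z₀.₉₀)² / (ln HR)².
- HR 0.7, no crossover: 4 × (1.960 + 1.282)² / 0.357² = 331 events (Freedman's formula: 338).
- 8% one-way crossover, with 8% of the CABG arm at the PCI hazard: HR = 0.92 × 0.7 + 0.08 = 0.724, giving 403 events (Freedman 410).
- 9%, the top of the stated range: HR 0.727, giving 414.

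So 414 is reproduced to within 3% at 8% and exactly at 9%, always with a constant HR. With 414 events and HR 0.724, power is 90.8%.

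**2. Events available.** The PCI hazard is −ln(0.30)/60 per month. Uniform 41-month accrual and 89 months in total give event probabilities of 0.740 (PCI) and 0.613 (CABG at HR 0.7): 315 × (0.740 + 0.613) ≈ 426. The events are reachable, so the issue is the effect pattern and not the count.

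**3. Early-excess patterns that reproduce the crossing.** Let the CABG hazard ratio be h for the first c months and 0.7 afterwards. The curves meet when the cumulative hazards are equal: h·c + 0.7(t − c) = t, so t = c(h − 0.7)/0.3. One-way crossover does not move t.

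**4. Power.** Simulated trials (4,000 per row, Monte Carlo SE at most about 0.6 points): 630 patients, exponential PCI arm with 70% events at 5 years, 41-month accrual, 89 months in total, 8% one-way crossover, log-rank without strata, two-sided 0.05, rejection in favour of CABG.

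| Early HR (months) | Curves cross at | Power |
|---|---|---|
| none (constant 0.7) | – | 92-93% |
| 1.6 (1) or 1.15 (2) | 3.0 months | 87-88% |
| 1.9 (1) or 1.3 (2) | 4.0 months | 85-86% |
| 2.2 (1) | 5.0 months | 83% |
| 1.5 (2) | 5.3 months | 82% |
| 2.5 (1), 1.6 (2) or 1.3 (3) | 6.0 months | 80% |

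For a given crossing time, how the early excess is spread hardly matters.

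**5. Stratifying the test** (constant HR 0.7).
- No prognostic difference between strata, no crossover: 95.5% without strata, 95.6% by presentation, 94.0% by centre × presentation.
- Presentation HR about 1.65, centre SD 0.3 on the log hazard, no crossover: 93.4%, 94.6%, 93.8%.
- Presentation HR 2.0, 8% one-way crossover: 89.8% without strata, 92.1% by presentation.
- Under the null with the moderate differences of the second case, the test without strata rejects in favour of CABG in 2.0% of runs (nominal 2.5%), so it is slightly conservative.
- Centre × presentation cells hold 630/(28 × 2) ≈ 11 patients, or 630/(35 × 2) = 9 with 35 centres. Under crossing curves (no crossover of treatment) that full stratification gives 81-86%, against 85-91% without strata.

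**The case against.** **The crossing may not carry over.** Section 1.33 rests on observational hospital data in a figure that is not shown. The time origin may also differ: the mortality definition in section 1.31 starts follow-up the day after operation, whereas section 1.17.1 counts from randomisation, with treatment weeks later in elective cases. This stands as a limit on the size. It does not remove the conflict, because the protocol offers these curves as its expectation for this outcome.

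**HR 0.7 may be meant as an average over follow-up.** The benchmark range of 0.63 to 0.74 comes from earlier trials' overall effects. On that reading the stated power could hold, but the later HR would have to be below 0.7, and section 1.16 does not say so.

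**There is a fallback, and a SAP is promised.** Both are true. A reader might infer that the alternative model would be picked after seeing unblinded data. The documents do not support that: the Statistical Analysis section has the SAP finalised before any analysis by treatment group, and section 1.58.5 has it published before data lock. What stands is that the fallback applies to the HR and not to the test that decides the trial.

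**The log-rank may yet be stratified.** A reader might conclude that it is definitely unstratified. Section 1.46 is merely silent, and strata are often left to a SAP. An unstratified test would also remain valid.

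**Early harm will be visible anyway.** Kaplan-Meier curves and 30-day events are reported. That helps description but supplies no pre-specified treatment contrast suited to crossing curves.

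**Conclusion.** The conflict between sections 1.16 and 1.33 is real. Under early-excess patterns that reproduce crossing at 3 to 6 months, power is about 88% falling to about 80%, against about 92% under a constant HR and 90% stated. This assumes an exponential PCI hazard, 8% one-way crossover, HR 0.7 after the early period, and an early excess of my choosing, since the protocol gives no size for it. Much lower power can be produced by front-loading the PCI events, for example 15% by 4.5 months. No passage supports that, and the design's constant hazard gives 1 − exp(−0.241 × 0.375) = 8.6%.

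Non-proportionality does not inflate type I error here. The damage is to power and to the interpretation of one HR.

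The stratification point is secondary: naming presentation as a stratum is worth about 1-2 points if presentation is moderately prognostic and nothing if it is not. No passage gives its prognostic strength.

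**What to change.** 1. **Section 1.16:** keep the constant-HR calculation and add the power under the crossing pattern of section 1.33, with the assumed early excess stated. Say whether 0.7 is the HR after the early period or an average over follow-up.
2. **Section 1.46:** commit to a restricted-mean-survival difference at 4 years, the minimum follow-up that every participant should have, and to HRs before and after a fixed early cut-point. Six months, the upper end of the range in section 1.33, is one option. Report both beside the Cox HR whatever the proportional-hazards check shows.
3. **Section 1.46:** specify the deciding log-rank as stratified by presentation, and handle presentation in the same way in the Cox model. Do not stratify the test by centre × presentation.

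The cost is wording only. Presentation is already recorded at randomisation, and no new data are needed. These changes do not restore the lost power. They make it visible, at the price of stating a less favourable figure, and leave the sponsor to decide whether that figure is acceptable.

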1.47 SECONDARY AND TERTIARY OUTCOMES AND SAFETY ANALYSES

Details of the analysis of the secondary outcome measures will be written in the SAP as described above and will follow the same principles as the primary outcome analysis with the exception of outcomes with potentially missing follow-up observations (e.g., PROMS) where a complete case analysis approach will be followed. Secondary outcomes will be reported similarly to the primary outcome using appropriate methodology, point estimates and confidence intervals to compare randomised groups; time to event outcomes using log-rank Kaplan-Meier and proportional hazards models, binary outcomes using logistic regression, continuous outcomes using linear regression or where not normally distributed using appropriate nonparametric methods.

Serious adverse event reporting is described in earlier sections and is largely for safety and ethics monitoring during the trial accrual and follow-up periods prior to statistical analysis taking place. AEs that meet the criteria for reporting as described above will be reported descriptively and summarised between groups based on the safety population (e.g., assigned to groups only if treated and according to treatment received).

1.48 INTERIM ANALYSES

No formal efficiency interim analyses are planned for this trial; no formal statistical rule for early termination of the trial is defined. One final efficacy analyses will be planned when all participants reach a minimum of 4 years follow-up. The independent DMC may observe the control arm event rate in the case it is substantially lower than expected, to allow recommendations to increase trial size and maintain adequate statistical power or advise futility. This observation will be blinded i.e., only control group or data overall to be presented and no outcome data will be presented that compares randomised groups.

1.49 SUBGROUP ANALYSES

A limited number of subgroups for the primary outcome measure will be pre-specified in the analysis plan and are likely to include sex (male versus female), age (<65 and \geq 65 years), acute versus chronic coronary syndrome, the extent of coronary disease (BCIS-1 JS <12 vs. \geq 12), degree of LV dysfunction (EF <30% vs. \geq 30%), diabetes, New York Heart Association (NYHA) class (<3 vs. \geq 3), and estimated glomerular filtration rate (eGFR) (<30 vs. \geq 30 ml/min/1.78m²). A Cox proportion hazards model (or appropriate alternative where assumptions are not met) incorporating tests of interaction will be used for subgroup analyses. The subgroup analyses will be exploratory.

1.50 MISSING VALUES

The primary outcome measures time until first event or censors at last follow-up therefore by definition there will not be any missing data. Other data adjusted for in the primary outcome analysis is a requirement of randomisation and therefore will not be missing. The use of routine and ONS data ensures we will have good long-term follow-up rates and early censoring due to loss to follow-up should be minimal at most and not expected at all. Analysis of non-time-to-event secondary outcomes like PROMs will be by complete case, the extent of missing data will be described.

HEALTH ECONOMIC EVALUATION

Evidence has shown that coronary heart disease cost £1.7 billion to the UK healthcare service, £2.4 billion in informal care, and £2.9 billion in productivity loss (34). The health economic evaluation will determine cost-effectiveness of CABG, compared with PCI, from the perspective of the UK NHS and personal social services, and the patient in line with the National Institute for Health and Care Excellence (NICE) guidance for health technology evaluation (35).

We will conduct the evaluation alongside the clinical trial over a minimum 4-year time horizon and a model-based evaluation over a lifetime horizon. We will capture all healthcare resource use utilised in both treatment groups over the duration of the trial. This will include resource use relating to treatment received (CABG and PCI), hospitalisations, cardiac outpatient visits and both paid and unpaid care received by the patient during follow-up. Hospitalisation data will be obtained from HES (as detailed in section 1.35). We will take key components of the iPCQ questionnaire relating to productivity and include these in the bespoke health resource use questionnaire. A focus group of National Cardiac Surgery PPI group members, led by our PPI co-applicants, identified the impact that HF can have on formal and informal carers as highly important. Therefore, the burden on formal and informal carers needs to be measured and incorporated in the health economic evaluation. Healthcare resource usage that is not captured by HES will be collected via a bespoke questionnaire, completed at baseline, three, six and twelve months and then annually thereafter until year four. For the within-trials analysis, mean total patient cost by trial arm will be estimated by applying national unit costs to healthcare resource use data. Health-related quality of life will be captured using the EQ-5D-5L questionnaire. EQ-5D-5L results will be mapped on to the EQ-5D-3L system using a “crosswalk” algorithm (36). Quality-adjusted life years (QALYs) gained will be estimated using the baseline-adjusted area under the curve approach (37). Where missing data are encountered, we will explore the assumptions regarding the missing data mechanism and decide upon an imputation method based on best practice (38). The mean total cost and mean total QALY gain per patient, according to randomisation group, will be estimated using a generalised linear model (GLM) and adjusting for trial minimisation factors and potential confounding factors. The appropriate family for GLM will be selected based on the results of the modified Park’s test. Cost-effectiveness at year four will be expressed as the incremental cost-effectiveness ratio (ICER) and net monetary benefit (NMB). We will assume a willingness-to-pay for QALY gains of £20,000. We will undertake probabilistic sensitivity analysis to explore the uncertainty in our results and plot the probability of cost-effectiveness on the cost-effectiveness acceptability curve (39). We will also undertake sensitivity analysis to explore the impact of our assumptions made regarding missing data by including a complete case analysis only. The impact of decision maker perspective will also be

explored in sensitivity analysis, by including productivity costs within an analysis from a societal perspective.

A lifetime health economic model will be informed by the existing literature in this area. An initial scoping review did not identify any lifetime cost-effectiveness analyses of CABG, compared with PCI, in patients with HF. We identified multiple studies that compared either CABG, PCI or medical therapy, in patients with coronary heart disease (40-43). Methods used ranged from within-trial only analyses, to lifetime models. Lifetime models typically extrapolated from the trial data using either parametric survival modelling or observational data. Resource use was obtained from clinical trial data, and where necessary for a lifetime analysis, from the literature or national cost records. The lifetime health economic model in this trial will capture disease progression using health states that represent the natural history of people living with HF. Based on the existing literature, it is likely to be a decision-analytic model with multiple health states in which a patient with HF experiences a monthly transition probability of experiencing further complications or death. We will apply a multivariable parametric survival model to the individual participant-level data to extrapolate the relevant clinical outcomes beyond the five-year trial period. The choice of parametric model will be based on visual inspection, Akaike (AIC) and Bayesian (BIC) information criteria goodness-of-fit statistics (44). Other relevant model parameters will be informed by a targeted literature review. We will undertake a probabilistic sensitivity analysis using a 10,000-iteration Monte Carlo simulation. To reflect uncertainty in our model's parameter values, each parameter will be characterised as a probability distribution, in oppose to a point estimate, allowing us to explore the extent to which uncertainty in model parameters feed through into uncertainty in final modelled costs, life years, QALYs and overall cost-effectiveness. Previous research has found CABG to be most cost-effective in patients with more severe forms of HF (40). Therefore, our analysis will stratify patients according to risk, based on LVEF (<35% vs \geq 35%), to explore the impact of heterogeneity in this patient population. As a scenario analysis, we will capture the wider economic burden on this patient population by undertaking the lifetime economic evaluation from a societal perspective.

TRIAL ORGANISATION, REGULATION AND OVERSIGHT

